## **5) RESOURCES AVAILABLE TO CONDUCT THE HUMAN RESEARCH**

Subjects will be recruited as part of normal SBIRT procedures already being conducted at the [name] General Internal Medicine site in Great Neck, NY. Normal SBIRT procedures include the pre-screening of all scheduled patients by medical assistants to identify initial substance use risks, and then further assessment to identify risk classification of the patient based on their substance use patterns and counseling by an SBIRT Health Coach for patients as needed based on this assessment. Patients identified as excessive drinkers during the standard SBIRT procedures will be asked by the SBIRT Health Coaches (HCs) about their interest in a study on treatment for problematic alcohol use in the primary care setting. As all clinic patients are being routinely screened for alcohol, we will have a large pool of patients screened from which to identify excessive drinkers. Based on SBIRT data collected, we estimate that 75% of the patients or about 33 per month have a primary alcohol problem and would not be excluded for other reasons. We estimate that about 2/3 of eligible participants would be classified as at-risk drinkers with the remainder in the other categories (i.e., Problem Drinkers, Alcohol Use Disorder with Physiological Withdrawal, and Alcohol Use Disorder with Chronic or Complex Presentation). Thus, assuming that 50% consent to participate, we estimate n=24 participants per month would be available to enroll in the study and about eight of these would meet problem drinking criteria. We note that of the 526 participants screening positive and offered a brief intervention at the [name] site, only 3 refused. Thus, we anticipate a positive response from participants and consider our recruitment projections as conservative estimates.

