## **7) ELIGIBILITY CRITERIA**

We expect to recruit a total of 85 participants for Phase I and II of this study based on the following inclusion/exclusion criteria:

**Inclusion Criteria:** Participants must: 1) receive care at the [name] General Internal Medicine clinic and/or other Northwell Health DGIM sites; 2) have an estimated weekly consumption of greater than 14 drinks for men and 7 drinks for women or experience

at least one binge drinking day (i.e., 5 or more drinks for men and 4 or more drinks for women) per week; 3) demonstrate observable fluency in English language; 4) have no recognizable cognitive impairment.

**Exclusion Criteria:** Participants will be excluded from the study if they: 1) report substance use other than cannabis, nicotine, or caffeine in the last year; 2) report using cannabis “daily or almost daily” and that this use is problematic and the primary concern compared to their alcohol use, as indicated in the SBIRT screening; 3) present with a serious psychiatric illness or substantial suicide or violence risk, as assessed via a chart review, reported by the primary care treatment team (e.g., the Primary Care Physician [PCP]), and/or reported by the potential participant in the initial screen; 4) are on probation or parole as reported in the initial screen; 4) have an organic mood/mental disorder; 5) is pregnant, breastfeeding, or trying to become pregnant as reported in the initial screen; 6) report being enrolled in current substance use treatment in the initial screen.

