## **10) ENDPOINTS**

Over the 12 weeks of the study, there will be five assessment points at weeks 0, 1, 4, 8, and 12, which all participants will receive. Participant response and safety will be assessed at each assessment point. In addition, participants will be monitored daily via Ecological Momentary Assessment data (EMA) comprising a brief questionnaire about their drinking. The HC will monitor participants' adherence to these surveys and their study visits and make outreach as needed. Notably, participant response to treatment will be assessed at week 4 and a stepped-care approach will be applied in the case that the participant has not responded to the initial treatment that he or she chose. For instance, participants who chose to receive a behavioral intervention will be offered medication (i.e., naltrexone) if they have not shown progress in their treatment as evident by a significant reduction in drinking.

Some participants will also attend treatment appointments in the 12 weeks of this study, some of which will overlap with the assessment appointments. Participants will have biweekly medication management appointments and/or potentially 4 to 12 sessions of behavioral treatment.

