**Week 0: Pre-enrollment:** Participants will be recruited through the Screening, Brief Intervention, and Referral to Treatment (SBIRT) program that is already a standard practice in the primary care site, where they are patients or to which they are referred to from other Northwell DGIM sites. As part of SBIRT standard practice in this setting, all patients are systematically screened for risky alcohol use by a medical assistant and a health coach, using the Alcohol Use Disorders Identification Test (AUDIT), a self-report validated screening tool. In addition, for patients who screen positive for risky alcohol use, the HC provides a brief intervention, which includes feedback about their drinking, a discussion about motivation to reduce use, and planning around reducing or stopping alcohol use. During this interaction, HCs will assess if patients are eligible for the study based on the criteria. The HC will provide a brief explanation of the study to patients who appear initially eligible to participate. Further eligibility screening will be provided either that day or another day when the patient is available, if he or she expresses interest in participating.

**Week 0: Eligibility Screening:** Participants will be recruited for this study based on our inclusion/exclusion criteria described above. Those participants who are interested in the study will be initially consented (General Consent) by the HC and will complete further measures (i.e., the Timeline Follow Back [TLFB] for the past 60 days and the Composite International Diagnostic Interview-Alcohol Module [CIDI-Alcohol]), assessing for drinking criteria and establishing risk classification for treatment options. Other inclusion/exclusion criteria (i.e., drug use, mental/organic disorders, suicide/violence risk, legal involvement, and pregnancy) will be evaluated at this point via self-report, chart review, and/or in consultation with the primary care clinical team (e.g., the primary care physician). Patients who endorse withdrawal criteria on the

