*Alcohol Use Disorder with Physiological Withdrawal Drinkers (AD-W)*: Participants meeting criteria for DSM-5 Alcohol Use Disorder with physiological withdrawal will receive outpatient detoxification as part of standard care, unless medically or socially contraindicated (described above). Upon completion of outpatient detoxification, participants will be offered 12 weeks of daily naltrexone plus medication management or 12, weekly sessions of **M o d i f i e d B e h a v i o r a l S e l f - C o n t r o l T h e r a p y ( M B S C T )**.

*Alcohol Use Disorder with Chronic or Complex Presentation Drinkers (AD-CMPLX)*: Participants in this group will include those who meet criteria for DSM-5 Alcohol Use Disorder, report inpatient treatment for alcohol use and/or other mental health issues within the last five years, experience social problems (i.e., unstable housing) that would suggest the need for more intensive psychosocial treatment, or are deemed not appropriate for outpatient detoxification treatment and in need higher-level of care as assessed by the NP/MD performing the CIWA-Ar assessment. Participants classified at AD-CMPLX will be referred to specialty substance use treatment based on the SBIRT protocol, where participants are referred to an outpatient treatment program that best fits their needs. In the case that these participants refuse a referral to specialty care, a second attempt will be made to do so at week 1. In the case that the second attempt is not successful, they will be offered MBSCT, abstinence-based treatment, focused on connecting them with specialty care, as part of the study.

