Once participants are grouped and offered treatment options for their risk classification, they will choose a preferred treatment course and be scheduled for their next appointment with an RN/NP/MD to administer naltrexone or a Behavioral Health Specialist (BHS) to conduct the behavioral interventions. Each respective clinician will complete either the Medication Intervention Consent or the Behavioral Intervention Consent with the participant at their next appointment. Notably, participants are free to change their treatment choice during the consent process (described below) with the clinician. If they do so, they will be scheduled for another appointment with the appropriate clinician. All participants will be informed that they are being asked not to pursue any other formal substance use treatment until after the week 12 assessment of the study, unless they are in the AD-CMPLX group and referred to treatment as part of this study. If they decide to pursue alternative treatment, study staff will facilitate referrals. The participant will continue to be followed in the study via follow up assessments in order to learn about the progress of the participant which is valuable in our effort to test a feasible treatment model.

**Weeks 1-12:** During this period, participants in the PD and AD-W groups will receive treatment (see procedure as follows) and assessments, while the AR and AD-CMPLX groups will be followed in assessments only. All groups will be assessed for appropriateness of stepped-care at week 4.

Participants, who choose the medication intervention, will attend medication management in-person at the primary care clinic. Appointments would be conducted by a NP, an MD, or an RN, who is supervised by an MD,. These appointments will occur weeks 1, 2, 4, 6, 8, 10, and 12. At their week 1 appointment after consent has been signed, the medical professional will assess the participant for appropriateness to take medications. They will conduct a medical exam, review the participant's chart, and may consult with his/her primary care clinical team.

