Participants who choose behavioral interventions will have appointments conducted at the primary care clinic or via televideo, based on the preference of the participant. Behavioral Health Specialists (BHSs), who are licensed therapists or therapists supervised by licensed clinicians, will conduct the treatment. Participants receiving MET will have four sessions at weeks 1, 2, 4, and 8. Participants receiving MBSCT will receive weekly sessions from week 1 to 12.

In addition to regular treatment appointments, follow up assessment appointments will occur with the HC at weeks 4, 8, and 12. Each assessment appointment will occur after the treatment session scheduled for that day. These appointments can occur in-person or via televideo based on each participant's preference and will be conducted by the HC. At each appointment, the participant will complete the Timeline Follow Back (TLFB), a treatment addendum, and patient satisfaction measures. Participants will be monitored for risk and safety at each of these appointments as described below.

Furthermore, at week 1, participants will meet with a HC to complete a demographics questionnaire and receive training and instruction on the Ecological Momentary Assessment (EMA; described below). Because participants will be using smartphones, we will show them how to use their phones in a way that increases the security and confidentiality of the online surveys and the texts they receive. Based on our experience in previous studies, participants complete about 80% of the required surveys, which is significantly higher than expected. Note that EMA data is in electronic format and available in real-time to the HC. We will monitor EMA diary completion continuously to increase compliance and will have the required data available

for safety monitoring. Participants will have the option to participate in the study even if they do not have a smartphone or refuse to use it to complete EMA. In such cases, participants will not complete EMA.

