perform a risk and safety assessment. Significant deterioration of note is defined as a significant increase in drinking since the baseline interview (more than 25%); a significant increase in depression, anxiety, or other mental health symptoms; instability in life circumstances that would suggest a need for immediate treatment; or suicidal or homicidal ideation. If any of these indicators are present, as a first-line of treatment, participants will be referred to the clinical team at the primary care clinic for additional treatment or evaluations. If a higher level of care is warranted, participants will be referred to appropriate care, such as intensive outpatient treatment, inpatient detoxification, or outpatient psychiatric treatment, and continued to be monitored at their assessment visits. For participants who present an imminent risk of harm to self or others, or an inability to care for themselves, the primary care clinical team will evaluate the patient to determine the need to activate EMS, who will then take the patient to the emergency room to be evaluated for possible inpatient psychiatric admission.

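### For participants detoxified after week 0, the 25% drinking rule does not register a return to their entry level, and no other numeric rule prompts referral at weeks 8 and 12 (low importance, cheap to improve)

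*Combined protocol and SAP*

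**What the plan says.** All in the combined protocol and SAP.

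- **Deterioration rule** (section 11, Risk/Safety Monitoring, applied at weeks 4, 8 and 12): "Significant deterioration of note is defined as a significant increase in drinking since the baseline interview (more than 25" per cent). The other indicators are worse mental health symptoms, unstable life circumstances, and suicidal or homicidal ideation. None of these has a number. The first response to any indicator is referral to the primary care clinical team.
- **Baseline drinking** (section 11, Week 0: Eligibility Screening): participants complete "the Timeline Follow Back [TLFB] for the past 60 days". The section 12 schedule lists this interview at weeks 0, 4, 8 and 12.
- **Order of events for AD-W** (section 11): week-0 measures come first, then detoxification, then study treatment. "Upon completion of outpatient detoxification, participants will be offered 12 weeks of daily naltrexone plus medication management", or weekly MBSCT sessions instead.
- **Absolute limits** (section 11, Weeks 1-12): a participant above 14 drinks per week (men) or 7 (women), or above the daily limits, is a non-responder. The action, stepped care, is tied to one visit: "All groups will be assessed for appropriateness of stepped-care at week 4".
- **Later visits** (section 10): "Participant response and safety will be assessed at each assessment point". No action is attached to non-response at week 8 or week 12.

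**The concern.** The rule compares current drinking with drinking at entry. That works for a participant whose drinking had not been changed by treatment before follow-up began. In AD-W, detoxification comes between the reference measurement and the first follow-up. A participant can stop drinking, relapse fully, and still read as unchanged.

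AD-W is the group defined by physiological withdrawal, so a return to heavy drinking after detoxification matters for safety. Inpatient detoxification is one of the referrals to which the deterioration rule can lead. At week 4 the absolute limits would usually pick up such a relapse. At weeks 8 and 12 no numeric rule with an action does so. No efficacy analysis is affected.

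**Working it through.** **1. Which baseline.** The term is not formally defined. I take it as the week-0 interview, because no other drinking interview is scheduled before week 4. The drinking measure used for the 25% is also unspecified; I use average drinks per week.

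**2. What the rule requires.** It is met only if current drinking > 1.25 × baseline. A return to baseline gives (B − B)/B = 0%, so it is not met at any B. The documents give no AD-W baselines. The values below are assumed for illustration.

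| Sex | Assumed baseline (drinks/week) | Must exceed (1.25 × B) | Multiple of weekly limit |
|---|---|---|---|
| Men (limit 14) | 24 | 30 | 2.1 |
| | 40 | 50 | 3.6 |
| | 60 | 75 | 5.4 |
| Women (limit 7) | 14 | 17.5 | 2.5 |
| | 30 | 37.5 | 5.4 |
| | 45 | 56.25 | 8.0 |

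If drinking is averaged over a 4-week interval with k abstinent weeks, the remaining weeks must average more than 1.25 × 4/(4 − k) times baseline. That is 1.67, 2.5 and 5 times for k = 1, 2 and 3.

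**3. Exception.** Suppose a of the 60 baseline days were abstinent, and the participant relapses to drinking every day at the earlier drinking-day level. The increase is 60/(60 − a) − 1: 25.0% at a = 12 (not met), 27.7% at a = 13 (met) and 42.9% at a = 18 (met).

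**4. How many people.** Section 5 puts about two-thirds of eligible participants in the at-risk group, so the three other groups together are at most about 85/3 = 28. Taking its 24 per month as given, 24 × 2/3 = 16 are at-risk and 8 remain. The same section says "about eight of these would meet problem drinking criteria", which leaves almost none for AD-W. Assumed AD-W shares of 2%, 5% and 10% give 85 × share = 1.7, 4.25 and 8.5 people.

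**5. Would a per-week trigger work?** One full week back at any baseline in the table exceeds the limit (24, 40, 60 > 14; 14, 30, 45 > 7). With even daily drinking, the relapse days needed within a 7-day block are 5, 3 and 2 for men and 4, 2 and 2 for women. Two alternatives do worse:

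- A 4-week mean misses 24 per week for two weeks (2 × 24/4 = 12), 40 per week for one week (40/4 = 10), and a woman at 14 per week for two weeks (7, not above 7).
- A single-day trigger fires too easily. With a daily chance q of one day over the limit, 1 − (1 − q)^28 = 25%, 43% and 76% at q = 1%, 2% and 5%.

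**6. How often it flags moderate drinkers.** Assume independent days and d = 2, 3 or 4 drinks per drinking day. Drinking days per week are binomial(7, mean/(7d)), and the flag rate per visit is 1 − (1 − P(week over limit))^4.

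| Sex | Mean drinks/week | d = 2 | d = 3 | d = 4 |
|---|---|---|---|---|
| Men | 4 | 0.0% | 1.5% | 4.0% |
| | 6 | 0.0% | 9.0% | 15.8% |
| | 10 | 0.0% | 56.8% | 61.4% |
| Women | 2 | 4.0% | 8.7% | 29.7% |
| | 3 | 15.8% | 23.6% | 52.0% |
| | 5 | 61.4% | 62.8% | 83.6% |

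An abstinent participant is never flagged.

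**The case against.** The strongest reply is that the rule does what it sets out to do. It defines deterioration as worsening since entry, and failure to improve is handled separately by absolute limits. That stands: the definition is not an error.

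A reader might infer that relapse after detoxification would go unnoticed. The documents do not support this:

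- Behavioral treatment brings frequent contact: "Participants receiving MBSCT will receive weekly sessions from week 1 to 12". Those on naltrexone are seen at least biweekly and asked about current drinking (section 13).
- Daily phone surveys of drinking reach the health coach in real time and are meant partly for safety monitoring, although participants may opt out (section 11).
- Section 11 commits Phase II to adjusting interventions for non-responders, without limiting this to week 4.
- Participants on naltrexone have a primary care physician visit at week 12 (sections 13 and 18).
- Sections 17 and 19 give clinicians a route to alternative or higher-level care.

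These safeguards are optional, unquantified or left to judgement, so they reduce the gap without closing it.

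The trigger is also non-specific. Section 13 allows a moderation goal, yet a woman averaging 5 drinks per week, under the limit, would be flagged at 61% to 84% of visits. That stands as a cost. Each flag is a real week above the protocol's own limit and leads only to an evaluation.

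**Conclusion.** The gap is real but of low importance. For AD-W participants who complete outpatient detoxification, the only quantified deterioration indicator for drinking is referenced to pre-detoxification levels. A return to the week-0 average does not meet it, and at weeks 8 and 12 referral then depends on clinician judgement. In the illustrations, drinking would have to reach 2.1 to 8.0 times the weekly limit before the rule is met.

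This rests on reading the baseline as the week-0 interview and on average weekly drinks as the measure. The size also rests on assumed baselines and AD-W shares, since the documents give neither. The group may be a few people or close to none. Because these phases are meant to shape the procedures for a later randomized trial, clearer wording has some value beyond this sample.

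**What to change.** Add one sentence to Risk/Safety Monitoring in section 11. For participants who completed outpatient detoxification, the first-line clinical-team evaluation at weeks 8 and 12 is also prompted if Timeline Follow Back drinks exceed the weekly limit (more than 14 for men, more than 7 for women) in any 7-day week since the last assessment, with weeks counted back from the assessment date.

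Label it as a return to drinking above limits that needs evaluation, not as deterioration. Let the evaluation take place at a visit already scheduled, such as the week-12 physician visit for those on naltrexone. Leave the 25% rule unchanged for everyone.

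The cost is protocol wording, because the data are already collected at both visits. At the assumed shares there are 1.7, 4.25 or 8.5 people × 2 visits = about 3, 9 or 17 checks, and at most 28 × 2 = 56. Some flags will fall on people who have cut down (for example from 60 to 16 per week), who have a moderation goal, or who declined stepped care at week 4. One case stays with clinician judgement: a participant who entered on "at least one binge drinking day (i.e., 5 or more drinks for men and 4 or more drinks for women) per week" and relapses to, say, one 6-drink day per week remains under the weekly limit.

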**Daily online questionnaires:** Ecological Momentary Assessment (EMA) is a global term used to describe techniques to collect data in the real world. For example, filling out a daily data diary would be considered a kind of EMA. For this study, EMA involves brief internet-based surveys. Participants will be asked to complete a brief, online survey every morning for the 11 weeks of participation (i.e., weeks 1 to 12). Participants will use their personal smartphone. Smartphones will be utilized for receiving text messages to prompt participants to complete the online survey. Each morning survey requires approximately one minute to complete and will ask about daily use of alcohol. We have used similar scripts previously (in our R01 study of MI), and they are attached to this protocol. Participants, who do not have a smartphone or wish to not use their smartphone as part of this study, will be free to opt out of this part of the study.

**Study Setting.** Whether participants are recruited from the [name] Primary Care Clinic or referred from another Northwell Health DGIM primary care site, this study will be conducted at the [name] site. It is located in Great Neck, NY, has been designated a Level 3 Patient Centered Medical Home (PCMH) since 2009. It was one of the first medical homes in the lower New York State region and includes both a faculty and resident practice with approximately 32,000 visits per year. Patients from a variety of socioeconomic and ethnic backgrounds are cared for by 16 faculty providers and 72 internal medicine residents. In addition to medical staff, the practice includes a clinical psychologist, 2 nurse practitioners, 2 social workers, a certified diabetes educator, a clinical pharmacist and a nutritionist. Medical assistants, nurses, and administrative staff support clinical staff members. These practitioners are part of the clinical team at this practice, and they provide regular monitoring/care for participants of this study. The practice uses the Allscripts electronic health record (EHR) and has since pioneered many of the innovations and enhancements including the use of e-calculators for SBIRT screens and generation of clinical alerts.

The National Center on Addiction and Substance Abuse (CASA) will contribute to the theoretical development of the study as well as data management and analyses. This will include participation in project meetings, performance of data analyses, and preparation of manuscripts. There will be no consenting or data collection that will occur at CASA. All recruitment, consenting, and subject data collection will be conducted at Northwell Health. Notably, the SBIRT project is being conducted in collaboration with CASA.

